7.0 Data and Specimen Banking

7.1 PHI will be stored on AWS in perpetuity. There is ongoing research on COVID-19 for the foreseeable future and this repository can be used for further research inquiries. De-identified data will be stored on GitHub and Zenodo in perpetuity. PHI collected by the web app will remain on AWS relational databases. The PI and key personnel will have access to the PHI and de-identified images. Other researchers will only have access to de-identified images for machine learning. We anticipate collecting 1,000 positive cases, with a total of 10,000-20,000 cases. All PHI will be stored on AWS including DocuSign Informed Consent and Medical Release Forms.

7.2 Data to be stored:

Survey questionnaire, Hospital site, and Deidentified DICOM imaging

7.3 Procedures to release data: Only GitHub data indexed by Zenodo will be shared to researchers. Only persons listed on the IRB will see PHI data on AWS.

Figure 1: Data Sharing

8.0 Sharing of Results with Subjects

8.1 Results of the study will not be shared with the subjects; however, subjects can log on to <https://CovidImaging.app> and view their radiographic image in DICOM format for their personal use.

9.0 Study Timelines*

9.1

Duration of subject's participation in the study: Subjects will be asked to provide informed consent and provide a medical release for each imaging site (estimated time burden \leq 30 minutes). Individual subjects can quickly fill out the surveys on the web app on their own time (estimated time burden \leq 30 minutes). Unless they choose to withdraw, subjects will remain in study repository indefinitely. Subjects will have choice to withdraw from the study at any time and will have the ability to delete their data permanently at any time, including their DICOM images.

- Duration anticipated to enroll all study subjects: One year
- The estimated date for the investigators to complete this study (complete primary analyses): December 2021

10.0 Inclusion and Exclusion Criteria

10.1 This study will include anyone in the country who has been tested for COVID-19 with a chest radiograph image. Patients will provide informed consent through the web application portal. The study will exclude adults unable to consent, individuals who are not yet adults (infants, children, teenagers) pregnant women, and prisoners.

11.0 Vulnerable Populations

11.1 N/A. The study does not plan to recruit minors (under age 18), pregnant women, prisoners, or adults who are unable to provide consent.

12.0 Local Number of Subjects

12.1 Subjects will be sourced online at <https://CovidImaging.app> from all across the US. We plan to collect 1000 positive images, and about 20,000 total images.

12.2 NA

13.0 Recruitment Methods

Subjects will be recruited online using social media advertisement campaigns designed to inform the general public about the project and invite eligible participants to join the study. Recruitment materials will direct potential subjects to a www.covidimaging.com, which will provide both study details and access to registration.

Recruitment on website www.covidimaging.com is worded as follows: “Countries like China have trained AI on state-curated centralized data-stores of radiographic imaging as part of a strategy to effectively halt their COVID-19 epidemics. However, in the US, , privacy regulations, lack of interoperability and active health information blocking has curtailed the availability of data to train clinical grade AI. While no country can match China in terms of its population size or its surveillance reach, we are crowdsourcing a COVID-19 Imaging Registry for our own AI research in the fight against COVID-19. Patients may donate their chest x rays and clinical data to our IRB-approved study. Patients’ images and related protected health information will be immediately deidentified to protect privacy, and patients may choose how their data may be used for research. We will use patients’ anonymized data to develop and deploy AI for digital triage of COVID-19. Please sign up now for more information, including on how to sign up to participate in the COVID-19 Imaging Repository research study.”

13.1 We have an informational site up at <https://CovidImaging.com>. We have a live beta app up at <https://CoidImaging.app>. We will not begin to enroll patients until we have IRB approval.

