The app collects this medical release form which is also PHI. Our app communicates the patient name, date of birth, imaging site, and MRN (when available) to the clinical provider to initiate the transfer. The medical release form collects PHI that will only be shared to initiate DICOM transfer. The clinical site ultimately sends the requested DICOM files, and we will specifically ask for all radiographic imaging for each potential COVID case. The patient will need to provide name and site, and MRN is optional. PHI (i.e. patient name) may be embedded on the delivered DICOM files. This is likely if clinical providers have scanned film with PHI labels embedded in images. We should not assume the clinical providers will strip the DICOM files because when Nautilus onboards the clinical provider, they become a business associate that can transfer PHI. This is a potential source of PHI leak on AWS. To address concerns, our study coordinators (as listed on the IRB application) will curate every image transferred to ensure no such images with PHI embedded are released for machine learning. Coordinators will annotate out the PHI manually before the image is released. We will use standard de-identification scripts to strip the DICOM files delivered to us of any PHI and integrate only raw .tiff or .png into our AWS web application.

We will keep/save the de-identified DICOMs on AWS to a secure S3 location, and MatrixRay will only communicate PHI to this AWS S3. AWS will only serve to coordinate PHI that we collect from the patient in EC2 instance independent from the S3 for imaging. EC2 serves to host our web applications and integrate imaging through transfer IDs. Once we receive their DICOM imaging, our app has a DICOM viewer that the patient can use to see their images. We will use MatrixRay on AWS to de-identify DICOM files by extracting images for machine learning. Only researchers and study coordinators approved by the IRB will curate de-identified images into labeled research imagesets that we will use for machine learning. PHI is not important to machine learning, so as a rule, we will keep all PHI we collect on AWS separate from any machine learning instances that will be either local at UCF or on Microsoft or Google clouds thereby protecting against any PHI leak.

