To maintain the separation of images from PHI, the web interface never shows explicit PHI (such as the patient name or MRN) on the same screen as an Image which further reduces the leak of PHI tied to images by screen shots or other untoward attempt.

Within our AWS app, we have embedded a UCF-managed Qualtrics backend to issue interactive surveys within our web app. We have developed an initial COVID-19 questionnaire to learn

clinical outcomes to predict from de-identified imaging. Future surveys will be issued once IRB-approved as we grow our app-based community. These surveys may be interactive and will allow for a platform where researchers can longitudinally follow patients through the rapidly evolving pandemic. By keeping this Qualtrics backend managed by UCF, we also minimize any PHI leaks.

As we develop AI models, we will publish de-identified labeled imagesets on Zenodo, which issues digital object identifiers (DOI) that can be cited in our research, with tight integration with GitHub to store de-identified image assets. We may issue imagesets for machine learning based on clinical outcomes or other features learned from patient surveys. Once de-identified assets are registered on Zenodo/GitHub, they will be maintained as open and accessible pending funding. We have at least three years of funding from [name] startup to maintain this repository, and we will be seeking NIH grants to develop the resource for the AI community in perpetuity.

The process can be outlined as follows:

1. Patient visit the informational covidimaging.com which directs them to sign up for app at covidimaging.app
 - a. Patient signs informed consent on DocuSign via app
 - b. App collects patient's full name and date of birth
 - c. App collects and validates patient's email address
2. Patient fills questionnaires about his/her imaging
 - a. App collects name, date of birth, site of imaging, medical record number, and date of imaging if available
 - b. Opens a new Transfer Ticket that serves to de-couple the PHI collected on the app from the imaging transferred
3. Patients fill out questionnaires about their COVID-19 course via app
 - a. Questionnaire asks about patient's clinical course, including molecular diagnosis of infection and convalescence
4. Web app sends email to the imaging site initiate DICOM transfer
 - a. No PHI is sent via email, just a notification that a new Transfer Ticket was created

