17.0 Data Management and Confidentiality

17.1 Describe the data analysis plan: Data will be maintained on AWS according to best practices.

17.2 Steps that will be taken to secure the data: Data will be de-identified according to HIPAA Safe Harbor method. PHI collected by the web app will remain on AWS relational databases. This PHI will index de-identified images will be stored on AWS S3 in perpetuity. Per HIPAA, PHI will be stored for a minimum of 6 years. Storage duration for signed consent, PHI release, self-reported questionnaires, and contact information will be stored for at least 6 years. The PI and key personnel will have access to the PHI and de-identified images. Other researchers will only have access to de-identified images for machine learning.

17.3 Describe how any study/participant numbers, pseudonyms, etc. will be generated: All numbers will be alphanumeric and randomly generated. Subject ID numbers will be generated sequential as C19AI001, C19AI002, ...etc.

17.4 Identifiers will be stored in perpetuity or until the subject has deleted their account and withdrawn from the study.

Per UCF policy, de-identified data will be retained for a minimum of 5 years following study closure.

Manual curation for quality control.

(See CovidImaging Data Flow diagram)

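### The recruitment text in 13.0 promises immediate de-identification, anonymized data and a choice of uses; the procedures keep linked identifiers and do not show the choice being applied

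*Protocol*

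**What the plan says.** Protocol 13.0 sets out the wording of the recruitment website. It tells prospective subjects that their images and the related PHI "will be immediately deidentified to protect privacy, and patients may choose how their data may be used for research". The next sentence describes the data used to build the AI as anonymized.

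Other sections describe what will be done:

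- **Storage (7.1):** "PHI will be stored on AWS in perpetuity", including the signed consent and medical release forms.
- **Linkage (17.2):** "This PHI will index de-identified images".
- **Limit on storage (17.4):** "Identifiers will be stored in perpetuity or until the subject has deleted their account and withdrawn from the study".
- **State of incoming files (6.1):** "PHI (i.e. patient name) may be embedded on the delivered DICOM files". The same paragraph recognises this as a possible leak.
- **Removal of embedded identifiers (6.1, repeated in 18.1):** "Coordinators will annotate out the PHI manually before the image is released".
- **Publication (6.1):** once de-identified assets are on Zenodo/GitHub, "they will be maintained as open and accessible pending funding".

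**The concern.** Section 6.2 names exposure of PHI as the only foreseeable risk to subjects. How identifiers are handled is therefore what a prospective subject most needs to be told correctly, and on that matter the recruitment text and the procedures disagree. A reader of the website would expect that no identifiable record remains after donation, that nobody can link images back to a person, and that uses can be selected. The procedures keep the identifiers and the link, and they describe no means of selecting uses.

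The stake for the repository is practical. If subjects donate expecting a choice of uses, and imagesets are assembled without checking that choice, the investigators cannot show that a published set respects what its donors were told.

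**Working it through.** No arithmetic applies. The check sets each recruitment statement beside the procedures.

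**1. Immediate de-identification.** The promise covers two things, the images and the related PHI.

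- *Related PHI.* The app collects name, date of birth, imaging site and, if available, record number (6.1, steps 1 and 2), together with the signed forms. Under 7.1 and 17.4 these stay identifiable until the subject deletes the account; 17.2 also sets a minimum retention of 6 years. No step de-identifies this material at any time, so the statement is false for PHI.
- *Images.* The figure legend in 6.1 says that scripts on the receiving client save only de-identified files, which comes close to the promise. Names burned into the image are handled differently: 6.1 and 18.1 leave them to manual annotation by coordinators, which must precede release but has no time limit. In the workflow, files arrive at step 5, the ticket closes at step 6, and de-identification of images with PHI appears, where applicable, at step 7. Section 15.1 also lists unauthorized access before de-identification and processing as a risk. The protocol thus concedes an interval that the recruitment text leaves out.

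**2. Anonymized data.** Section 17.2 makes the retained PHI the index to the images, and 6.2 speaks of patient information being encoded. Two features of the design need that link: subjects can view their own images in the app (8.1), and account deletion removes a subject's images, including from GitHub and Zenodo (14.1, 14.3). Data that the study team can trace to a named person are coded, not anonymized.

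**3. Choice of use.** The eight steps in 6.1, read for any point at which permitted uses are recorded or checked:

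| Step | Content | Use recorded or checked? |
|---|---|---|
| 1 | Sign-up, consent, identity, email | Not described; 1a is the consent signature, form not shown |
| 2 | Imaging questionnaire, ticket opened | No |
| 3 | COVID-19 course questionnaire | No |
| 4 | Notice to imaging site | No |
| 5 | Image transfer | No |
| 6 | Ticket closed | No |
| 7 | Imagesets assembled and published | No |
| 8 | Model training and validation | No |

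The release rule in 7.3 limits what is shared to the GitHub data indexed by Zenodo and mentions no subject-level restriction. The only control described for the subject is complete withdrawal with deletion (9.1, 14.1 to 14.3). That is a choice between all and nothing, whereas 13.0 offers a choice of how data are used.

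**The case against.** The strongest reply is that 13.0 is an advertisement. It invites people to sign up for further information; the decision comes later, at informed consent with comprehension questions (22.1). The consent form is not among the documents reviewed, and a data-use option would naturally sit there. This stands as a limit on the point: a reader might infer that the study offers no choice at all, or that subjects are misinformed when they consent, and the documents support neither. It does not rescue the advertisement, which should agree with the protocol whatever the form says. Nor does it supply the missing check at release, since an option recorded on a form but not consulted at step 7 would have no effect.

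Second, scripted de-identification on receipt makes the promise nearly true for most images. That is fair, and it confines the image part of the contradiction to embedded identifiers. It leaves the stored PHI untouched.

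Third, indefinite storage ends on account deletion, machine-learning instances are kept apart from PHI (6.1, 18.1), and outside researchers receive only de-identified images (7.1, 17.2). All of this is correct, and for those outside researchers the data may be anonymous in effect. Within the study they are not.

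Stronger readings that the text does not carry:

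- *Open release cannot be undone.* Section 14.3 promises deletion from GitHub and Zenodo. The fate of copies already downloaded is not addressed, so irreversibility would be an assumption.
- *Anyone may use the images for any purpose.* Section 6.1 says they are open and 7.3 says they are shared with researchers; no licence terms are given.
- *Open publication itself breaks the de-identification promise.* It concerns de-identified images only, and bears on the choice clause alone.

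**Conclusion.** The recruitment wording is wrong as written on two statements and unsupported on a third. *Immediately* is contradicted by retained identifiable PHI and by manual removal of embedded identifiers. *Anonymized* is contradicted by the index that links PHI to images. The choice of uses is promised, but no workflow or release step visible in the protocol applies it.

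The size cannot be put as a number of people. The wording reaches everyone recruited through the website. A reader might take the planned 10,000 to 20,000 as a subject count, but 1.0 and 7.1 call these cases, 12.1 speaks of about 20,000 images, and 6.1 requests all radiographic imaging for each potential case.

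The conclusion on the first two statements rests on the protocol alone. The conclusion on the third is limited to the protocol's procedures and would narrow to the missing release check if the consent form does record permitted uses. No endpoint, sample size or analysis changes. The point should still be corrected, because it concerns the one foreseeable risk the protocol names and the correction is cheap.

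**What to change.** Reword the website text in 13.0 so that it states three things:

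1. Images are de-identified on receipt, with manual review for embedded identifiers before release.
2. Identifiers are kept and linked to the images by code until the subject deletes the account.
3. De-identified images are published openly.

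Delete *immediately* and *anonymized*.

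For the choice of uses, take one of two routes. Either delete the clause, or keep it, add a data-use field at step 1a, and check that field before each imageset is released at step 7, with a matching line in 7.3. In both cases, compare the consent form with the revised text so that the two agree.

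The cost is an IRB amendment to the recruitment material and, on the second route, one additional field and a filter at release. The plainer text may recruit slightly fewer people.

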14.0 Withdrawal of Subjects

- 14.1 At any time and for any reason subjects can delete their account on <https://Covidlaging.app> which will automatically withdraw them from the repository and delete all of their data. This is permanent and cannot be undone. However, subjects can re-enroll again and at any time.
- 14.2 Procedure for orderly termination: Subjects may log on to <https://Covidlaging.app> and delete their account.
- 14.3 If a subject withdraws from the study, all the subject's data and images will be permanently deleted from our servers including GitHub and Zenodo.

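### Withdrawal promises permanent deletion, GitHub and Zenodo included, but the release and retention sections carry no matching exception and downloaded copies cannot be recalled

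*Protocol*

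**What the plan says.** On withdrawal, the protocol is generous in three places. Section 9.1 says subjects "will have the ability to delete their data permanently at any time, including their DICOM images". Section 14.1 says a subject may delete the account, "which will automatically withdraw them from the repository and delete all of their data", and calls this permanent. Section 14.3 names the public platforms: "all the subject's data and images will be permanently deleted from our servers including GitHub and Zenodo".

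On release and retention, it points the other way. Section 6.1 states that "we will publish de-identified labeled imagesets on Zenodo, which issues digital object identifiers (DOI) that can be cited in our research", and then: "Once de-identified assets are registered on Zenodo/GitHub, they will be maintained as open and accessible pending funding". Section 7.1 says: "De-identified data will be stored on GitHub and Zenodo in perpetuity". Section 7.3 makes the GitHub data indexed by Zenodo the copy that researchers receive. Section 17.2 sets a 6-year minimum for signed consent, release forms, questionnaires and contact information. Section 17.4 sets a 5-year minimum after study closure for de-identified data.

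**The concern.** Section 14.3 and section 7.1 name the same two platforms and give opposite instructions for a withdrawn subject's images. Staff handling a withdrawal cannot follow both as written.

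Two things are at stake. The first is a right stated to subjects. After an open release, the team controls the hosted files but not what others have already taken from them, and 14.1 promises deletion without that qualification. The second is objective 2, training and validating COVID-NET. The imagesets are to be cited by DOI. If images are removed from a cited set after a result is reported, the set that a reader retrieves is no longer the set that was analysed, and nothing in the protocol says how the difference would be recorded.

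**Working it through.** The protocol states no figure to reproduce, so the check sets the passages side by side.

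**1. Does each retention or release provision yield to withdrawal?**

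- 6.1, registered assets: kept open, and the only stated limit is funding. No withdrawal exception.
- 7.1, de-identified data on GitHub and Zenodo: no time limit. No withdrawal exception.
- 17.2, consent, release forms, questionnaires and contact data: at least 6 years. No withdrawal exception.
- 17.4, de-identified data: at least 5 years after closure. No withdrawal exception.
- 17.4, identifiers: kept only until the subject deletes the account and withdraws. Exception present.
- 9.1, presence in the repository: indefinite unless the subject withdraws. Exception present, in general terms.
- 25.1, subject data: available until the account is deleted or the repository is dissolved. Exception present, in general terms.

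The likely intention is that withdrawal overrides retention for copies the study hosts. The sections that govern the published sets and the minimum periods do not say so. The 6-year minimum in 17.2 conflicts directly with 14.1 for questionnaires, consent and contact data.

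**2. Suppose withdrawal prevails. What can be deleted?**

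- Hosted copies on AWS, GitHub and Zenodo: 17.2 indexes images by PHI, so the study can locate a subject's images. Whether either public platform allows removal is not stated in the documents.
- Working copies: 6.1 refers to "any machine learning instances that will be either local at UCF or on Microsoft or Google clouds". Section 14.3 does not name these, although they fall within the broad wording of 14.1.
- Copies downloaded by others: these are outside the team's control. This follows from open release itself and needs no outside fact.
- Models already trained: deleting image files does not undo their earlier use in training. The protocol says nothing on this.

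The promise to delete all data is therefore wrong once a set containing the subject's images has been released, whichever section is given precedence.

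**3. What happens to a cited set?** If 14.3 is carried out, the contents behind the DOI change. If it is not, 14.3 is breached. For hosted copies these are alternatives, and the protocol does not say which applies. It has no rule on versions or on recording changes.

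**4. Size.** The protocol plans 1,000 positive cases and 10,000 to 20,000 in total (sections 1.0 and 7.1), but gives no withdrawal rate or release date. Purely as an illustration, assume that 1% to 5% withdraw after release:

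- Positives: 0.01 × 1,000 = 10 to 0.05 × 1,000 = 50.
- All cases: 0.01 × 10,000 = 100 to 0.05 × 20,000 = 1,000.

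The rate is an assumption, and the point does not depend on it.

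**The case against.** The best defence is that the protocol should be read as a whole. Section 9.1 makes the indefinite stay conditional on not withdrawing, 25.1 ends availability at account deletion, and 14.3 is the specific rule for the same two platforms that 7.1 names. On that reading, perpetuity is the default and 14.3 the exception. Section 6.1 does not promise perpetuity for registered sets either, since "they will be maintained as open and accessible pending funding" is a weaker commitment. This stands as a reading of intent. It does not settle 17.2 or the de-identified data in 17.4, and it does not reach copies already downloaded.

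Several stronger readings are tempting, and the documents do not support them:

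- *The promise in 14.3 cannot be kept at all.* Its wording concerns the team's servers and the two hosted platforms. Deletion there is not shown to be impossible. Only the unqualified promise in 14.1 and 9.1 fails, and only after release.
- *Cited sets will change without notice.* The protocol is silent on notice and does not say that changes go unannounced. The exact statement is that it has no versioning rule.
- *Subjects consent to a right that the design lacks.* Section 22.1 refers to a consent form that is not available here, so what subjects are told cannot be confirmed.
- *Withdrawal fails against the one named risk.* The risk in 6.2 is exposure of protected health information, and 15.1 places unauthorized access before de-identification. Published sets are meant to be de-identified. Section 6.1 does acknowledge that identifying labels may be embedded in delivered images and relies on manual curation to remove them, but that does not show that released sets contain them.

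**Conclusion.** The point holds in a limited form. The withdrawal sections (9.1, 14.1, 14.3) and the release and retention sections (6.1, 7.1, 17.2, 17.4) are not reconciled. For hosted copies this is a drafting conflict, and 9.1 and 25.1 indicate how it was probably meant to be resolved. After open release, the unqualified promise in 14.1 exceeds what the design can deliver, because downloaded copies and trained models cannot be recalled. Carrying out 14.3 also changes the set behind a reported training or validation result, with no provision for recording the change.

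No effect on any model result has been shown, and the number of subjects affected cannot be derived. The conclusion rests only on the protocol's wording and on the fact that an open release can be copied. It should be fixed before the first public release, since released copies cannot be retrieved afterwards.

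**What to change.** 1. Restate 9.1, 14.1 and 14.3 by timing. Before release, withdrawal deletes all of the subject's images. After release, the images are removed from every hosted copy under the team's control (AWS, GitHub, Zenodo and the machine-learning copies) and are not used in later training, but downloaded copies and trained models cannot be recalled. Align the consent wording, and confirm with both public platforms that removal is possible before promising it.

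2. Add an exception for subjects who withdraw to 6.1, to 7.1 and to the de-identified data retention in 17.4. Reconcile the 6-year minimum in 17.2 with 14.1 by stating which records are kept after withdrawal.

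3. Release imagesets only as numbered, dated versions. On withdrawal, issue a new version without the images, remove the image files from earlier hosted versions, and keep a non-identifying record of what changed. State the version used with each reported result.

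The cost is protocol and consent wording plus version control of releases. There are two downsides. The withdrawal right reads less generously to subjects. A result obtained on an earlier version can no longer be reproduced exactly after a withdrawal, although the difference is documented.
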